### *Rationale for the Study Design*

#### *Open-label Design*

The open-label design allows patients who completed the full treatment period in the IEDAT-02-2015 and all its assessments (or were discontinued from the Study IEDAT-02-2015 during the COVID-19 pandemic), to continue treatment as long as their physician determines they are not experiencing any adverse effects that would necessitate discontinuation of treatment and do not present safety contraindications to continuation of treatment. This study also gives patients who were receiving placebo treatment in the prior study the opportunity to start treatment with EDS-EP.

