#### 11.4.2 Baseline visit (Visit 1/ Day 0)

Final evaluations for IEDAT-02-2015 study (Visit 15/Month 12) will serve as baseline evaluations for patients continuing in IEDAT-03-2018 study. The following "baseline" assessments for IEDAT-03-2018 will be done as part of the final Visit 15 evaluation in Study IEDAT-02-2015: physical/neurological examination; 12-lead standard ECG; laboratory evaluations [including hematology, clinical chemistry, urinalysis, serum pregnancy test (women of childbearing potential); special laboratory tests: HbA1c, CD4+ lymphocytes count and CRP]; assessment of physical development, sexual maturation, and the effect of treatment with dexamethasone on these aspects (Tanner scale); ICARS; CGI-S; CGI-S; EQ-5D-5L; C-SSRS; BMD; review of AEs and concomitant medications.

- a) Obtaining written informed consent (before any study procedures)
- b) Check of the demographic information, medical history, previous and concomitant medications, ongoing adverse events and non-drug therapies and procedures (demographic information, medical history rolled over from IEDAT-02-2015 eCRF)
- c) Vital signs [including height and weight measurements in triplicate at baseline; calculation of BMI, temperature (oral or tympanic, according to the specific medical practice of the Center), pulse, systolic and diastolic BP, and respiratory rate].
- d) Hemolysis panel (including urinalysis), on the diverted blood samples (see Section 11.5)

Patients providing informed consent or assent and meeting the eligibility criteria will receive study treatment prepared and administered as follows:

- e) 1 mL blood collected, after blood diversion (see Section 11.5), for aerobic culture
- f) Autologous blood collection for EDS processing
- g) Addition of the assigned study medication (DSP) to the EDS process
- h) Upon completion of the EDS process, fill the satellite sample bag CCI [REDACTED] if no other samples but the ones for sterility culture test will be collected).
- i) Study treatment administration by IV infusion, within 30 min after the EDS process has been completed.
- j) CCI [REDACTED]  
[REDACTED]  
[REDACTED]  
[REDACTED]  
[REDACTED]  
[REDACTED]  
[REDACTED]  
[REDACTED]

Before the EDS-EP infusion, patients (women of childbearing potential) must undergo a pregnancy urine test. All patients should undergo assessment of prior and concomitant medication and AEs.

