### 3.3 Study Schedule

#### Screening phase

The screening phase is *applicable only for patients which will be enrolled without completing the ATTeST trial. The screening phase will last a maximum of 30 days. Any previous treatments with corticosteroid compounds will be withdrawn (washout from previous treatment), while for other patients the screening phase may coincide with the screening visit (1 day long, provided that all the required laboratory reports are available and reviewed before the eligibility confirmation at the baseline). As soon as all screening assessments/procedures have been performed and eligibility is confirmed, the patients can undergo the baseline visit.*

*If any abnormal laboratory test results, vital sign measurements, or ECG findings of clinical significance are noted at the screening visit, these must be repeated during the 30-day screening period and the results made available prior to making the final decision on a patient's eligibility for the study at Baseline.*

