### 6.3 Subgroup Definitions

Patients are grouped by their treatment group in the ATTeST study: EDS-EP Low Dose, EDS-EP High Dose, Non-switch Placebo, Visit 9 Low Dose, Visit 9 High Dose, Visit 12 EDS-EP Low Dose, and Visit 12 High Dose. All outputs contain columns to display these groups.

The following endpoints are also summarised by subgroups for Age (<10; ≥10 years) and Region (India; Europe, Australia, and Tunisia; United States):

- ICARS
- mICARS
- RmICARS
- CGI-C
- CGI-S
- EQ-5D-5L

Patients with a treatment gap of greater than 76 days between the ATTeST study and the OLE-IEDAT study are presented as a separate subgroup for outputs as outlined in Section 10.

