### Date of First Infusion of Active Treatment

The Date of First Infusion of Active Treatment is defined as the earliest infusion of active study drug, including infusions from the ATTeST study. For patients in the Non-Switch Placebo group

this will equal the date of first OLE-IEDAT Infusion. For all other patients this date will be received by CROMSOURCE in ADaM datasets from ATTeST.

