## 7.4.8 Safety Variables

### Adverse Events

*An adverse event (AE) is defined as any untoward medical occurrence in a patient or clinical investigation subject administered a pharmaceutical product and that does not necessarily have a causal relationship with this treatment. An AE can therefore be any unfavorable and unintended sign (including an abnormal laboratory finding), symptom, or disease temporally associated with the use of a medicinal (investigational) product, whether or not related to the medicinal (investigational) product.*

Adverse events data are collected from the time that informed consent is given until 30 days after the final visit (Month 12 or early discontinuation) or at least 60 days after final infusion, whichever is longer, on the 'Adverse Events' eCRF page.

The AE Description (Investigator term) is coded to a Lower-Level Term (LLT), a Higher Level Term (HLT), a Preferred Term (PT) and a System Organ Class (SOC) using MedDRA.

AEs' intensity is recorded as "Mild", "Moderate" or "Severe". any AE with a missing intensity is considered "Severe".

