### Treatment-emergent adverse events (TEAEs)

A treatment-emergent adverse event (TEAE) is defined as an AE that started or increased in severity on or after the date of first Study Treatment Administration. All AEs that occur during this OLE-IEDAT study are defined as TEAE as all patients received study treatment in the IEDAT-02-2015 study.

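### The SAP counts every extension-study AE as treatment emergent, including AEs before any EDS-EP in patients who had only placebo, and AEs before the first infusion fall in no 12-month period

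*SAP*

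**What the plan says.** SAP 7.4.8 (Treatment-emergent adverse events) gives two rules in succession. The first depends on onset: a TEAE is "an AE that started or increased in severity on or after the date of first Study Treatment Administration". The second has no onset condition: "All AEs that occur during this OLE-IEDAT study are defined as TEAE as all patients received study treatment in the IEDAT-02-2015 study".

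Other parts of the documents bear on the second rule:

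- SAP 6.3 shows results by ATTeST group; the list begins "EDS-EP Low Dose, EDS-EP High Dose, Non-switch Placebo, Visit 9 Low Dose, Visit 9 High Dose".
- SAP 7.1 says of the date of first active infusion in the Non-switch Placebo group that "this will equal the date of first OLE-IEDAT Infusion". The protocol agrees (7.3, Open-label Design): "This study also gives patients who were receiving placebo treatment in the prior study the opportunity to start treatment with EDS-EP".
- SAP 7.4.8 (Adverse Events): "Adverse events data are collected from the time that informed consent is given".
- SAP 3.3, on patients who did not complete ATTeST: "The screening phase will last a maximum of 30 days". The protocol synopsis ties the 30 days to patients washing out other corticosteroids; for the rest, screening can be a single day.
- Protocol 16.2.5 plans to summarise events that are new or worse after study drug has been given. SAP 3.6, which lists departures from the protocol, does not mention the all-AEs rule.
- SAP 7.1 (Intervals from First OLE-IEDAT Infusion) opens the first 12-month AE period at Day 0. SAP 10.7.1 presents the AE overview overall and again by period.

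**The concern.** The reason given for the all-AEs rule is prior study treatment. It is literally true only if placebo counts as study treatment, and placebo cannot make an event emergent on EDS-EP. In a placebo-only patient who enters through screening, the rule turns AEs that precede the drug into TEAEs.

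Safety is the primary objective, and the related, serious, fatal, discontinuation and special-interest tables are built on the TEAE flag. The Non-switch Placebo column is also the only one that shows first exposure to EDS-EP within this study. One feature of the window makes it sensitive: corticosteroids are withdrawn during screening, and the AESI list in SAP 7.4.8 includes signs of adrenal insufficiency. A withdrawal symptom recorded before any EDS-EP could therefore appear as an AESI on EDS-EP.

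The second problem is the period table. SAP 7.1 (Study Day) foresees events before the first OLE infusion, which get a negative day, but no 12-month period accepts a negative day.

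**Working it through.** There is no sample size, power or error rate to reproduce; the study is descriptive. The check sets the two TEAE rules against the period windows.

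**Windows.** The five listed periods follow [365k, 365k + 364] for k = 0 to 4, and all five reproduce. For k = 4 this gives days 1460 to 1824. Since 1460/365 = 4 years (48 months) and 1825/365 = 5 years (60 months), the printed label of 48 to 62 months should read 48 to 60.

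**Classification by onset day**, for a Non-switch Placebo patient, counted from the first OLE infusion (also the first EDS-EP infusion):

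| Onset day | First sentence of the TEAE paragraph | Second sentence | 12-month period |
|---|---|---|---|
| -30 | not a TEAE | TEAE | none |
| -15 | not a TEAE | TEAE | none |
| -1 | not a TEAE | TEAE | none |
| 0 | TEAE | TEAE | 0 to 12 months |
| 364 | TEAE | TEAE | 0 to 12 months |
| 365 | TEAE | TEAE | 12 to 24 months |

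The two sentences disagree on every negative day, and those are the days without a period. The missing period applies to every ATTeST group. In groups already exposed to EDS-EP, TEAE status on a negative day can be defended, but the event still has nowhere to go in Table 14.3.1-1.1.2.

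**Who has negative days.** By schedule, patients who completed ATTeST consent at the baseline visit, Day 0 (Protocol 11.1 and 11.4.2). A same-day AE then satisfies both sentences and falls in the first period. A multi-day window arises by schedule only for patients with a screening phase.

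**Scale** (assumptions: ATTeST at its minimum of 180, the planned thirds, and equal roll-over from all groups to the expected maximum of 150):

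- Placebo arm: 180/3 = 60. Not switched before Month 12: 60/3 = 20, or 20/180 = 11.1%.
- Non-switch Placebo entrants: 150 × 20/180 = 16.7, about 17. This is the whole group. Those affected are the members who came in through screening, a number the documents do not give.
- Pre-exposure time at the 30-day maximum: 5 such patients give 5 × 30 = 150 patient-days (0.4 patient-years); all 17 would give 17 × 30 = 510 (1.4 patient-years).
- In a column of 17, one patient counted wrongly moves a percentage by 1/17 = 5.9 points.

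**Consistency with the rest of the SAP.** The date imputation in 7.2.2 separates pre-treatment from treatment-emergent onset; under the all-AEs rule that step does nothing for AEs. The off-dose rule in 7.4.8 (Adverse Events During COVID-19 treatment interruptions) says AEs more than 60 days after the last dose are not treatment emergent, so the word all also fails within the same section.

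**The case against.** The strongest reply is that the rule over-includes. It adds events to the safety tables and hides none, nothing is tested, and the AE listings carry onset dates and derived days, so pre-infusion events remain identifiable. All of that stands, and it limits the importance of the point. It does not make the rule correct: tables of emergent events should not contain events that precede the drug, and the SAP's own first sentence says so.

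It can also be said that the off-dose rule might already remove some screening AEs of patients discontinued during the pandemic. It might, but the SAP does not say whether that rule covers the gap between ATTeST and the OLE.

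A third reply concerns the remedy. SAP 7.1 counts an infusion towards the first OLE date only if it began within 30 minutes of the end of the EDS process. If the first infusion began later than that, the anchor date would move to a later visit, and AEs after real exposure would be labelled pre-treatment. This is right, and the fix below avoids that date.

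A reader might infer four stronger points that the documents do not support:

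- *Unresolved ATTeST AEs are re-counted here.* Protocol 11.4.2 asks for a check of "previous and concomitant medications, ongoing adverse events and non-drug therapies and procedures", but does not say these are entered again as OLE AEs. The same section restricts the post-infusion AE assessment to events after consent, and SAP 7.4.3 records current as well as past conditions as medical history.
- *Events are counted twice in the NDA.* SAP section 9 leaves the NDA outputs to a separate document, and nothing describes pooling AEs across the two studies.
- *The periods ought to add up to the overall column.* The overview counts patients, so someone with TEAEs in two periods appears in both; the columns would not add under any definition. The gap is only that some events have no period.
- *About 17 patients are affected.* That figure is the size of the whole Non-switch Placebo group, not of the part that had a screening phase.

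**Conclusion.** The point holds in a limited form. The all-AEs sentence classifies AEs before any EDS-EP as treatment emergent in placebo-only patients who entered through screening, against the sentence before it and against Protocol 16.2.5. Separately, AEs before the first OLE infusion, in any group, have no 12-month period.

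The effect is on descriptive counts and is probably small. The window is at most 30 days by schedule and can be one day. The patients concerned are an unstated subset of about 17 of 150, a figure that rests on the planned ATTeST allocation and proportional roll-over. It is still worth correcting before the tables are run, because it touches the primary safety tables and a small column in which one patient shows.

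**What to change.** In SAP 7.4.8:

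- Replace the second sentence of the TEAE paragraph with a rule of this kind: a TEAE is an AE with onset or worsening on or after the date of the first EDS-EP infusion actually started, in ATTeST or in the OLE, whether or not that infusion met the 30-minute condition of SAP 7.1.
- Reconcile this with the 60-day off-dose rule, and say whether that rule covers the gap between ATTeST and the OLE.
- List OLE AEs before that date as pre-treatment.
- State how worsening is dated. Protocol 14.1.2 lists onset, stop and intensity but no date of worsening; the existing first sentence has the same need.

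In the period outputs:

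- Add a before-Day-0 row to Table 14.3.1-1.1.2. It is needed in the previously exposed groups even after the TEAE rule is repaired.
- Correct the label for days 1460 to 1824 in SAP 7.1 to 48 to 60 months.

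The cost is one sentence of SAP text with its reconciliation, one derivation from recorded infusion dates, and one table row. The TEAE count becomes slightly lower; no data are lost, since the earlier AEs stay in the listings.

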### Serious Adverse Events

A Serious Adverse Event (SAE) is any adverse event *that at any dose:*

- *Results in death,*
- *Is life-threatening, i.e., an event which, in the view of the Investigator, places the subject at immediate risk of death from the event as it occurred (it does not include an event which hypothetically might have caused death if it were more severe)*
- *Requires inpatient hospitalization or prolongation of existing hospitalization,*
- *Results in persistent or significant disability/incapacity,*
- *Is a congenital anomaly/birth defect (if exposure to product just before conception or during pregnancy resulted in an adverse outcome in the child), or*
- *Is an important medical event that may jeopardize the subject or may require medical intervention to prevent one of the outcomes listed above.*

Treatment-emergent SAEs (TEAEs) are derived as any TEAE flagged as serious on the 'Adverse Events eCRF' page. Any TEAEs with a missing serious flag are regarded as serious.

### Adverse Events of Special Interest (AESIs)

Adverse Events of Special Interest include the following:

- Potentially steroid-related TEAEs
  - Low bone mineral density
  - Low CD4 count
  - Itching
  - Osteopenia
  - Osteoporosis
  - Weight gain
  - Cortisol suppression
  - Glaucoma

- Stunt growth
- Infections
- Hyperglycemia
- TEAEs indicative of adrenal insufficiency
  - Extreme fatigue
  - Weight loss and decreased appetite
  - Darkening of skin (hyperpigmentation)
  - Low blood pressure, even fainting
  - Salt craving
  - Hyponatremia
  - Hyperkalemia
  - Low blood sugar (hypoglycemia)
  - Nausea, diarrhea or vomiting
  - Abdominal pain
  - Muscle or joint pains
  - Irritability
  - Depression
  - Confusion
  - Body hair loss or sexual dysfunction in women

These are identified by a manual review of all AEs.

The findings of the manual review are documented in an excel spreadsheet provided by EryDel which is used to select AESIs from the clinical database.

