### 13.5 Special Laboratory Evaluations

Measurement of selected “special” laboratory parameters has been included in the study to evaluate potential effects of dexamethasone (EDS-EP) treatment (for details on aseptic procedure for blood withdrawal and on blood diversion see “Study Procedures on Sterility Testing for Study IEDAT-03-2018 (OLE-IEDAT)”; [Appendix 9](#)). The following special laboratory parameters will be assessed in the study:

- Blood glycosylated hemoglobin (HbA1c, %), CD4+ lymphocytes and C-reactive protein (CRP)– to be performed at Months 6 and 12.
- Screening for adrenal insufficiency will be performed in all patients, regardless of weight, via early morning (before 8:00 AM) plasma cortisol testing at the following times: (1) when patients are symptomatic, and (2) when patients are at most risk for adrenal insufficiency and adrenal crisis, such as following discontinuation or interruptions of dexamethasone dosing (i.e., loading failures and following discontinuation of the study drug). If the 8:00 AM cortisol level is below 3-5 µg/dL (depending on assay) regardless of symptoms, or the patient exhibits signs or symptoms of adrenal insufficiency ([Appendix 12](#)) and has a cortisol <10 µg/dL, the patient will receive a high dose ACTH stimulation test, regardless of weight, within 24 hours. If the ACTH stimulation test is normal, the patient can continue dosing with EDS-EP, after the effects of the ACTH have dissipated (e.g., 30 days after ACTH administered). If the patient fails the ACTH stimulation test they will be discontinued from the study and referred to a pediatric endocrinologist, with a recommendation to prescribe stress dose steroids.

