#### **Adverse Events During COVID-19 treatment interruptions**

For patients with treatment interruptions that result in gaps in dosing of greater than 60 days, adverse events are only considered treatment emergent if they occur within 60 days following the last dose. Adverse events that occurred greater than 60 days following the last dose will not be considered treatment emergent. For this population of patients whose long treatment interruption was due to COVID-19, three types of summarizations will be prepared:

- On dose (treatment emergent) adverse events
- Off dose (not treatment emergent) adverse events. Off dose events are those that occur during a period >60 days following a dose and prior to the immediately following dose.
- Restart (TEAE after restart of treatment) adverse events. Restart events are those that occur on/after the first dose after an off-dose period and prior to the start of any following off dose period.

Times to be considered as treatment interruptions due to Covid-19 are provided by EryDel in form of an excel spreadsheet.

|   |         |  |
|---|---------|--|
| CD+4 Lymphocyte count   | x10E9/L | Month 6 and Month 12   |
| Early morning Plasma Cortisol testing for Adrenal Insufficiency | µg/dL   | As needed: when patients are symptomatic, and when patients are at most risk for adrenal insufficiency and adrenal crisis, such as following discontinuation or interruptions of dexamethasone dosing |
| High dose ACTH stimulation test                                 | µg/dL   | As needed: In the event that patients show signs or symptoms of adrenal insufficiency during the study  |

All laboratory assessments are performed at local laboratories. Quantitative laboratory results are converted to their respective Reporting units for use in summary tables. Assessment of results as being within the normal range are made by the local laboratory. *Any laboratory abnormalities meeting the definition of an adverse event should be recorded on the Adverse Events CRF.*

Clinically notable values of standard laboratory are derived based on SI units as outline in Appendix 13.1.

If repeat tests are performed at any visit the result documented under the nominal visit label is used in all summaries and analyses for that Visit.

Baseline is as described in Section 7.1.

The change from baseline is calculated for quantitative laboratory tests at each scheduled post-baseline visit as:

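### The adrenal-insufficiency AESI group is restricted to TEAEs, but the SAP contradicts itself on whether events beyond day 60 of a long dosing gap are treatment emergent; on one reading they leave the AESI table

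*SAP*

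**What the plan says.** SAP 7.4.8 names two AESI families: potentially steroid-related events, and "TEAEs indicative of adrenal insufficiency". On how they are found it says "These are identified by a manual review of all AEs"; the sponsor records the outcome in a spreadsheet that then selects AESIs from the database.

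Two rules in the same section decide what is treatment emergent:

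- The general definition: "All AEs that occur during this OLE-IEDAT study are defined as TEAE as all patients received study treatment in the IEDAT-02-2015 study".
- The COVID-19 interruption rule, which opens "For patients with treatment interruptions that result in gaps in dosing of greater than 60 days" and then states: "Adverse events that occurred greater than 60 days following the last dose will not be considered treatment emergent". It adds: "Off dose events are those that occur during a period >60 days following a dose and prior to the immediately following dose". Events after dosing restarts are treatment emergent again.

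The output specifications are split in the same way. The list of summaries in SAP 10.7.1 labels the off-dose summary treatment emergent. In SAP 12.1, Tables 14.3.1-1.9 (on dose) and 14.3.1-1.11 (restart) carry that label, but Table 14.3.1-1.10 (off dose) does not. The title of the AESI table, 14.3.1-1.4, does not mention treatment emergence.

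Protocol 13.5 requires early-morning cortisol testing for any patient with symptoms. It also requires it "when patients are at most risk for adrenal insufficiency and adrenal crisis, such as following discontinuation or interruptions of dexamethasone dosing". It spells this second case out as "loading failures and following discontinuation of the study drug".

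**The concern.** A treatment-emergent filter suits toxicity that arises on drug. Adrenal insufficiency after steroid withdrawal arises when drug is absent, and the protocol itself places the greatest risk after interruption or discontinuation. An AESI group that stops counting 60 days into an interruption would leave out part of the period for which it is most relevant.

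The primary objective is long-term safety and tolerability of a steroid product. A low adrenal AESI count could then partly reflect the definition. Because the SAP states both rules, two programmers could also follow it faithfully and produce different versions of Table 14.3.1-1.4 and of the line for patients with at least one AESI in the overview, including its repeats by 12-month period.

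**Working it through.** The plan gives no event count, rate or gap length for this point, so there is no figure to reproduce. The check sets the texts side by side and then counts days.

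**1. Is an adverse event on day 61 or later of a long gap treatment emergent?**

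| Text | Answer |
|---|---|
| SAP 7.4.8, general TEAE definition | Yes, as for every AE in the extension |
| SAP 10.7.1, list of summaries | Yes, by label |
| SAP 7.4.8, COVID-19 interruption rule | No |
| SAP 12.1, title of Table 14.3.1-1.10 | Not labelled treatment emergent, unlike Tables 1.9 and 1.11 |

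**2. Consequence for the adrenal group**

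- If the general definition governs, the word TEAEs in the AESI heading removes nothing.
- If the interruption rule governs, an adrenal-type event from day 61 until the day before the next dose is outside the group. It is then absent from Table 14.3.1-1.4 and from the AESI overview count.
- The interruption rule is the more specific text and the table titles follow it, so it is the likelier one to be programmed. That is a judgement; no text says which rule prevails.

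**3. Days affected under the interruption rule**

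Inputs: the longest permitted interval between infusions is 38 days and the shortest is 21 (SAP 7.1); the cut-off is 60 days (SAP 7.4.8). Let g be the number of days from one dose to the next.

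- Days outside the AESI group: later than day 60 and before day g, which is g − 61.
- Days of interruption beyond the permitted interval: later than day 38 and before day g, which is g − 39.

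The gap lengths below are assumptions.

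| g | g − 61 | g − 39 | Share |
|---|---|---|---|
| 60 | 0 (no day exceeds 60) | 21 | 0% |
| 76 | 15 | 37 | 41% |
| 90 | 29 | 51 | 57% |
| 120 | 59 | 81 | 73% |
| 180 | 119 | 141 | 84% |
| 365 | 304 | 326 | 93% |

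**4. The interruptions that the protocol spells out**

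- One loading failure, meaning one missed infusion: the gap runs from 2 × 21 = 42 to 2 × 38 = 76 days, so 0 to 15 days are affected.
- Permanent discontinuation: the safety visit falls 53 to 67 days after the last infusion (SAP 7.1, Table 2). AE collection runs to at least 60 days after the last infusion, or to 30 days after the final visit if that is later (SAP 7.4.8). The cut-off therefore nearly coincides with required follow-up.
- Days 1 to 60 of any gap, and all restart events, remain treatment emergent under both rules.

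**5. Where off-dose events still appear**

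They appear by system organ class and preferred term in Table 14.3.1-1.10 and in the AE listings. Cortisol, ACTH and adrenal screening results have their own listings (16.2.8-1.5 to 1.7). None of these outputs is planned with an AESI breakdown. The adrenal list ranges over fatigue, electrolyte, gastrointestinal, joint and psychiatric terms, so it would scatter across organ classes. The number of patients with an adrenal AESI could not be read off the off-dose table.

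**The case against.** The strongest reply is that nothing has been shown to be excluded. The general definition makes every AE in the extension treatment emergent, the manual review covers all AEs, and the AESI table title carries no restriction. On that reading Table 14.3.1-1.4 is complete. This stands as far as it goes: a reader might infer that the plan definitely drops these events, or that the TEAE wording harms this group whichever rule prevails, and the documents support neither. It does not remove the problem, because the interruption rule is equally explicit and more specific. Reviewing all AEs says where reviewers look; the heading says what they keep.

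Second, the protocol's own examples of high-risk interruptions are loading failures and discontinuation, not pandemic gaps, and for those examples little time is lost. This also stands. The protocol's broader phrase does cover interruptions of dosing, so long gaps are not outside its concern.

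Third, a reader might take the 57% to 93% figures as the proportion of adrenal events lost. They are shares of assumed calendar time. Protocol 14.4 puts the half-life below 4 days, so day 60 lies at least 60 / 4 = 15 half-lives after dosing, and nothing in the documents supports a constant risk through a long gap.

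Fourth, the events are reported elsewhere, so the withdrawal period is not censored from the report. That is correct; what would be missing is their identification as AESIs.

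Finally, most terms on the list are non-specific, and counting all off-dose time would bring in background illness. This is a real cost, and the reason to show the periods separately.

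**Conclusion.** The point holds as an unresolved contradiction in the TEAE definition that feeds a key safety group. If the interruption rule governs, adrenal-type events from day 61 of a gap over 60 days until the next dose are left out of Table 14.3.1-1.4 and the AESI overview count. If the general definition governs, nothing is left out.

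The effect is confined to patients with gaps over 60 days. It is nil to 15 days for one missed infusion and small after permanent discontinuation. It covers most of the time beyond the permitted interval only in long gaps, for example 119 of 141 days in an assumed 180-day gap. The SAP plans for a population with COVID-19 gaps over 60 days but gives neither their lengths nor any adrenal event rate, so the number of events affected cannot be derived. The text should be corrected because a stated rule could undercount this group in a study whose primary objective is long-term safety, and the correction is cheap.

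**What to change.** 1. Reconcile the general TEAE definition and the COVID-19 interruption rule in SAP 7.4.8 with the off-dose entry in SAP 10.7.1, so that one rule applies and the table titles match it.
2. In SAP 7.4.8, define the group as: *AEs indicative of adrenal insufficiency that started or worsened on or after the first OLE-IEDAT infusion, regardless of treatment-emergent status.* This settles the group whichever TEAE rule is kept.
3. In Table 14.3.1-1.4, show the group overall and, for patients with long interruptions, split into on-dose, off-dose and restart periods. Base the AESI overview count on the same definition.

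The cost is a sentence or two of text and extra columns in an existing table. The three periods are already to be derived and all AEs are already to be reviewed, so no new data are needed and no clinical rule changes. The adrenal count may rise, by an amount that cannot be stated in advance, and will include some non-specific background events; the split keeps these visible. The group would also rest on a different basis from the steroid-related AESI family in the same table, which a footnote should say.
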